### **Tumor response from IWG Criteria 2014, Lugano Classification**

For patients who have their tumors additionally measured by positron emission tomography computerized tomography (PET-CT) scan, tumor response (CR, PR, SD, and PD) assessed centrally as defined by the IWG Criteria 2014, Lugano Classification, will be descriptively summarized and TTE will also be calculated using the same method as for TTE in efficacy analyses, except based on the FASEXP and PPSEXP sets.

## **17. Safety Outcomes**

All outputs for safety outcomes will be based on the SAF.

There will be no statistical comparisons between the treatment groups for safety data.

### **17.1. ADVERSE EVENTS**

Adverse events (AEs) will be coded using MedDRA 22.0.

A TEAE will be defined as any AE with an onset date (and time if applicable) on or after the date (and time if applicable) of first dose of study drug until Week 52, or the EOS visit, if earlier. AEs with increased severity during the treatment period will be considered as TEAEs whether already present during the pre-treatment period or not. Pre-existing AEs before the treatment period with no increase in severity during the treatment period will not be considered as TEAEs.

See Appendix 1 for handling of partial dates for AEs. In the case where it is not possible to define an AE as treatment emergent or not, the AE will be classified by the worst case; i.e. treatment emergent.

For AE table summary, patients will be counted at most once for each PT and each SOC.

---

Document:

Author:

Version Number:

Version Date:

Final v1.0

10Sep2019

Template No: CS\_TP\_BS016 Revision 4

Effective Date: 01Apr2016

Reference: CS\_WI\_BS005

SOCs will be presented alphabetically; PTs will be sorted within SOC in descending order of subject frequency across both treatments (Total). If the frequency of the PT is tied, the PTs will be sorted alphabetically.

AEs occurring between consent and first dose and AEs with an onset more than 60 days after the end of treatment, i.e., last study drug date + 1 days (as defined in section 12.1 of this SAP), will not be summarized (unless they are related or AESIs), but they will be listed. All AEs will be listed.

### **TEAEs**

Incidence of TEAEs will be summarized by the number and percentage of patients experiencing events by SOC and PT.

### **Severity**

Severity will be assessed according to the National Cancer Institute-Common Terminology Criteria for Adverse Events (NCI-CTCAE) v4.03. A TEAE with a missing NCI-CTCAE severity grade will be classified as missing. If a patient reports a TEAE more than once within that SOC/PT, the AE with the maximum NCI-CTCAE severity grade will be used in the corresponding severity summaries. TEAEs will be summarized separately by SOC, PT, and severity group.

### **Relationship to Study Drug (Causality)**

The causal relationship between the study drug and the AE should be defined as unrelated or related. TEAEs with a missing relationship to study drug will be regarded as “related” to study drug. If a patient reports the same AE more than once within that SOC/PT, the AE with the worst case relationship to study medication will be used in the corresponding relationship summaries.

A summary of related TEAEs starting on the day of the infusion or the day after the infusion will be presented.

### **TEAEs Leading to Discontinuation of Study Drug**

TEAEs leading to permanent discontinuation of study drug are identified by choosing ‘Drug permanently withdrawn’ in the question ‘Action taken with study drug’ on the Adverse Events page of the eCRF, and will be summarized by SOC and PT.

### **TEAEs Leading to Study Drug Interruption**

TEAEs leading to study drug interruption are identified by choosing ‘Drug interrupted’ in

---

Document:

Author:

Version Number:

Version Date:

Final v1.0

10Sep2019

Template No: CS\_TP\_BS016 Revision 4

Effective Date: 01Apr2016

Reference: CS\_WI\_BS005

the question 'Action taken with study drug' on the Adverse Events page of the eCRF, and will be summarized by SOC and PT.

### **Serious Adverse Events**

Serious adverse events (SAEs) are identified by choosing 'Yes' in the question 'Is the adverse event serious' on the Adverse Events page of the eCRF. A summary of serious TEAEs by SOC and PT will be prepared, and all SAEs will be listed.

### **TEAEs Leading to Death**

TEAEs leading to death are identified by choosing 'Yes' in the question 'Resulted in death' on the Adverse Events page of the eCRF. TEAEs leading to death will be summarized by SOC and PT, and listed.

### **TEAEs of Special Interest (AESI)**

AESIs to be considered in this study are: progressive multifocal leukoencephalopathy (PML), hepatitis reactivation, infusion reactions, anaphylactic reactions, mucocutaneous reactions and serious infections (see study protocol section 6.4 for more details). These group terms are each separately identified on the eCRF.

The incidence of TEAEs of special interest are identified by choosing 'Yes' in the question 'Is this event an AESI (Adverse Event of Special Interest)' on the Adverse Events page of the eCRF. TEAEs of special interest will be summarized by SOC and PT, and listed. Additionally, TEAEs of special interest to infusion reactions will be summarized by SOC and PT.

### **TEAEs Related to Immune-response**

The incidence of TEAEs related to immune-response are identified by choosing 'Yes' in the question 'Is this AE 'immune-response-related' of the Adverse Events page of the eCRF. TEAEs related to immune-response will be summarized by SOC and PT, and listed.

All AEs will be listed.

## **17.2. DEATH**

Information relating to patients who die during the study is recorded on the Death Information page of the eCRF. The information will be presented in a summary table and a data listing.

---

Document:

Author:

Version Number:

Version Date:

Final v1.0

10Sep2019

Template No: CS\_TP\_BS016 Revision 4

Effective Date: 01Apr2016

Reference: CS\_WI\_BS005

### 17.3. LABORATORY EVALUATIONS

Results from the laboratory test will be included in the reporting of this study for hematology (including erythrocyte sedimentation rate), clinical chemistry (including C-reactive protein and rheumatoid factor), virology, and urinalysis parameters.

Presentations will use SI Units (where applicable). Unit conversions will be performed by Data Management (DM) in the database where necessary.

Quantitative laboratory measurements reported as “< X”, i.e. below the lower limit of quantification, or “> X”, i.e. above the upper limit of quantification, will be converted to X for the purpose of quantitative summaries, but will be presented as recorded, i.e. as “< X” or “> X” in the listings.

The following summaries will be provided for laboratory data:

- Actual and change from baseline by visit (for quantitative measurements).
- Shift table of incidence of abnormal values (abnormal low, normal, abnormal high), based on normal range, from baseline to each post-baseline visit for hematology, clinical chemistry, and urinalysis parameters.
- Abnormalities by visit and overall abnormalities incidence result will be summarized, and further break down by high/low abnormalities. Patients will be counted at most once for a high or low abnormality for hematology and chemistry parameters.
  - Overall abnormal: Patient with at least one abnormal (high or low) result in post-baseline visit regardless the baseline result.
  - Overall normal: Patient without any abnormal result in all post-baseline visits regardless the baseline result.
- Listing of all laboratory test values (hematology and chemistry) with the abnormal values flagged with H (high) or L (low).

The following figures will be provided for laboratory data:

- Actual values by visit will be presented using a box plot for hematology and clinical chemistry. Mean +/- SEM by visit will be provided for hematology and clinical chemistry.

---

Document:

Author:

Version Number:

Version Date:

Final v1.0

10Sep2019

Template No: CS\_TP\_BS016 Revision 4

Effective Date: 01Apr2016

Reference: CS\_WI\_BS005

- Shift from Baseline for hematology and clinical chemistry.
  - For liver function tests (LFTs), the reference tick marks will be 3x ULN, 5x ULN and 10x ULN. Possible Hy's Law cases will be listed.
  - For other hematology and chemistry, the reference tick marks will be: 3x LLN, 2x LLN, 1x LLN, 1x ULN, 2x ULN and 3x ULN

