8.9.2 Clinical Laboratory Evaluations

Summary statistics will be presented for observed values of all hematology, chemistry, and urinalysis parameters at each visit with a laboratory assessment and at EOS, and also for changes from baseline to each post-baseline visit with a laboratory assessment and EOS.

Shifts (abnormal low, normal, and abnormal high) from baseline to each post-baseline visit with a laboratory assessment and EOS, based on normal ranges, will be presented for hematology, chemistry, and urinalysis parameters.

The incidence of laboratory abnormalities overall will also be presented. Where applicable, the incidence of abnormal values will be presented separately by whether the value is abnormally high or low. Patients will be counted at most once for a high or low abnormality for each laboratory parameter.

Listings of all laboratory abnormalities will be presented (separately for hematology and blood chemistry parameters). Laboratory ranges used to identify abnormal results will be provided by the local laboratory.

Listings of observed values of all hematology, chemistry, and urinalysis parameters, as well as pregnancy test results will be presented.

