### **Laboratory Normal Ranges**

Quantitative laboratory measurements will be compared with the relevant laboratory normal ranges in SI units:

- Abnormal high: Higher than the laboratory reference range upper limit.
- Normal: Within the laboratory reference range (upper and lower limit included).
- Abnormal low: Lower than the laboratory reference range lower limit.

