### Vital Signs Clinically Significant Abnormal Criteria

Clinically significant abnormal quantitative vital signs measurements will be identified in accordance with the following clinically significant abnormal criteria:

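### In SAP 17.3, two of the three low-side marks on the laboratory shift figures lie above the lower limit of normal, and no described laboratory table grades how far blood counts fell

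*SAP*

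**What the plan says.** SAP 17.3 plans shift-from-baseline figures for hematology and clinical chemistry and fixes the marks to be drawn on them. Liver tests are handled separately: "For liver function tests (LFTs), the reference tick marks will be 3x ULN, 5x ULN and 10x ULN". For everything else the instruction is "For other hematology and chemistry, the reference tick marks will be: 3x LLN, 2x LLN, 1x LLN, 1x ULN, 2x ULN and 3x ULN".

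The same section defines the low side by a single boundary: "Abnormal low: Lower than the laboratory reference range lower limit". Its shift table uses three classes: "Shift table of incidence of abnormal values (abnormal low, normal, abnormal high), based on normal range, from baseline to each post-baseline visit". Abnormalities are also counted by visit and overall, split only into high and low.

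Protocol 8.9.2 plans the same structure. Shifts are in three classes by normal range, and "the incidence of abnormal values will be presented separately by whether the value is abnormally high or low".

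SAP 17.3 also provides observed values and changes at each visit, box plots, mean plots with standard errors, and a full listing with high and low flags. SAP section 7 refers to separate table, figure and listing templates, which are not part of the available text.

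**The concern.** A reference mark on the low side should help the reader see how far below normal a value has fallen. Marks at two and three times the LLN cannot do that. They look like the multiples of the upper limit (ULN) copied across to the lower limit, though that is an inference about how the line arose.

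The low side matters for this drug. Protocol 1.3 lists hematological toxicities among the risks of rituximab, and safety is a secondary objective (Protocol 2.2). Protocol 4.9 makes dosing depend on neutrophil and platelet thresholds, so the plan itself treats depth as clinically relevant. If neither the figures nor the tables separate a mild from a deep fall, the two arms can be compared on low counts only as low or not low, or by reading distributions and listings.

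**Working it through.** There is no planned figure to reproduce here. The check is arithmetic on the marks, followed by a comparison of the described outputs.

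**Step 1: position of the marks.** For k > 1 and LLN > 0, k × LLN > LLN. With ULN > LLN, the six marks fall as follows: below the LLN, 0; on it, 1; above it, 5 (2x and 3x LLN and the three ULN marks). Of the three marks meant for the low side, 1 is usable and 2 are not. If ULN < 2 × LLN for an analyte, then 3 × LLN > 2 × LLN > ULN, and both marks lie above the whole normal range. An LLN of 0 is the only exception, and it does not apply to neutrophils, platelets or hemoglobin.

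**Step 2: illustration.** The documents give no laboratory ranges, so every LLN below is an assumption. The values 120, 1.5 and 100 are borrowed from protocol cut-offs (FLIPI-2 hemoglobin and the cytopenia limits in inclusion criterion 3). The values 2.0 and 150 extend the range.

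| Analyte | Assumed LLN | 2x LLN | 3x LLN | 1/2 LLN | 1/3 LLN |
|---|---|---|---|---|---|
| Hemoglobin, g/L | 120 | 240 | 360 | 60 | 40 |
| Neutrophils, ×10⁹/L | 1.5 to 2.0 | 3.0 to 4.0 | 4.5 to 6.0 | 0.75 to 1.0 | 0.50 to 0.67 |
| Platelets, ×10⁹/L | 100 to 150 | 200 to 300 | 300 to 450 | 50 to 75 | 33 to 50 |

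The planned multiples all lie above the LLN. The fractions all lie below it.

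**Step 3: what each described output shows on the low side.**

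| Output | Depth below the LLN |
|---|---|
| Shift table (Protocol 8.9.2, SAP 17.3) | None; one low class |
| Abnormality counts, by visit and overall | None; one low class |
| Shift figures | No mark below 1x LLN |
| By-visit summaries | Raw distribution (Protocol 8.5 includes the minimum); no counts by depth |
| Box plots, mean plots | Raw distribution; no counts by depth |
| Listing | Every raw value, flagged high or low; not graded |
| Adverse events by severity (SAP 17.1) | CTCAE grade, only for events reported as such |

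**Step 4: consequence for the counts.** Protocol 4.9 requires platelets of at least 75 ×10⁹/L before each subsequent dose. With an assumed LLN of 100 to 150, that threshold is 75/150 = 0.50 to 75/100 = 0.75 of the LLN. A count below it and a count just under the LLN fall in the same class.

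The shift table can also miss worsening. Inclusion criterion 3 admits patients with hemoglobin from 100 g/L. With an assumed LLN of 120 g/L, a hypothetical patient who starts at 105 and falls to 75 (75/120 = 0.625 of the LLN) moves from low to low, which is no shift.

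**The case against.** The strongest reply is that the marks are an editorial slip. They remove no data, the 1x LLN mark is right, and no count or classification depends on the other two. Protocol 8.9.2 never promises graded laboratory values, and the SAP delivers what it does promise. Investigators must also review every laboratory result and report a clinically important change as an adverse event (Protocol 5.2.5 and 6.7). For those events, "the AE with the maximum NCI-CTCAE severity grade will be used in the corresponding severity summaries". All of this stands. It narrows the gap to low counts that are not reported as adverse events, but it does not make the two marks correct.

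A reader might infer more than the documents support:

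- **That depth is hidden.** It is not. By-visit summaries, box plots and listings show it; what is missing is a count of patients by depth.
- **That vital signs get better treatment.** SAP 17.5 says "Clinically significant abnormal quantitative vital signs measurements will be identified in accordance with the following clinically significant abnormal criteria", but its Table 3 gives one low and one high post-baseline threshold per sign. That is the same three-class structure. The liver-test multiples are likewise only figure marks, on the high side.
- **That late cytopenias drop out.** SAP 17.1 says that adverse events starting more than 60 days after treatment "will not be summarized (unless they are related or AESIs), but they will be listed". This follows the collection rule in Protocol 6.8 and 6.9 and does not limit the laboratory tables.
- **That retest handling conceals low values.** SAP 5.3 lets unscheduled results count towards worst-case values where required. Whether a retest replaces a lower value in by-visit summaries depends on how sites number repeats, which the documents do not show.

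**Conclusion.** The point holds, at minor severity. Two of the three low-side marks are wrong for any positive LLN. That needs no assumption about laboratory ranges.

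The second part is narrower. In the protocol and SAP text, low neutrophil, platelet or hemoglobin values not reported as adverse events are not graded by depth in any described table. Because the templates were not seen, a graded table may exist there, so this part is limited to the text. The documents do not allow an estimate of how many deep falls would go ungraded, or of any difference between arms.

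The effect is confined to descriptive safety displays. The Week 28 response-rate equivalence test and the pharmacokinetic comparison are unaffected.

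**What to change.** In SAP 17.3, replace the marks at 3x and 2x LLN with marks below the LLN. Either CTCAE v4.03 cut-points or fractions such as 0.5x LLN would serve. Fractions suit an axis scaled to each local laboratory's limit, and cut-points suit an axis in absolute units; the SAP does not say which is planned.

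Add one descriptive table by arm of worst post-baseline CTCAE v4.03 laboratory grade against baseline grade, for neutrophils, platelets and hemoglobin. State that the worst value is taken over all scheduled, unscheduled and retest results to Week 52. The Week 28 report would carry the table to its own cut-off and the Week 52 addendum would complete it.

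The cost is a short SAP edit, one corrected figure axis, one extra table and a little programming. The data are already collected, CTCAE v4.03 is already in use for adverse events, and no protocol change is needed.

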### **Laboratory Normal Ranges**

Quantitative laboratory measurements will be compared with the relevant laboratory normal ranges in SI units:

- Abnormal high: Higher than the laboratory reference range upper limit.
- Normal: Within the laboratory reference range (upper and lower limit included).
- Abnormal low: Lower than the laboratory reference range lower limit.

## **17.4. 12-LEAD ECG EVALUATION**

The following summaries will be provided for ECG data:

- Incidence of ECG evaluation results by visit
- Listing of all ECG evaluation results.

## **17.5. VITAL SIGNS**

The following vital signs measurements will be reported for this study:

- Systolic blood pressure (mmHg)
- Diastolic blood pressure (mmHg)
- Pulse (beats/min)
- Body Temperature (°C)
- Respiratory Rate (breaths/min)

---

Document:

Author:

Version Number:

Version Date:

Final v1.0

10Sep2019

Template No: CS\_TP\_BS016 Revision 4

Effective Date: 01Apr2016

Reference: CS\_WI\_BS005

- Weight (kg)

The following summaries will be provided for vital signs and weight data:

- Actual and change from baseline by visit and time point
- Shift table of incidence of significant abnormal values (low, normal, high), based on the criteria listed as below, from baseline to each post-baseline visit.
- Abnormalities by visit and overall abnormalities incidence result will be summarized and presented for all parameters, and further broken down by high/low abnormalities. Patients will be counted at most once for a high or low abnormality for each vital sign parameter.
  - Overall abnormal: Patient with at least one abnormal (abnormal high or abnormal low) result in post-baseline visit regardless of the baseline result.
  - Overall normal: Patient without any abnormal result in all post-baseline visits regardless of the baseline result.

A Listing of vital signs will be provided with results meeting clinically significant abnormal criteria marked as High (H) or Low (L)

### Vital Signs Specific Derivations

For Body Temperature (°C), the oral, axillary and tympanic routes will be considered as equivalent and no conversions will be applied. The conversion from Fahrenheit to Celsius will be made as follows:

- $T(^{\circ}C) = (T(^{\circ}F) - 32) \times 5/9$ : degrees Celsius (°C), degrees Fahrenheit (°F)

### Vital Signs Clinically Significant Abnormal Criteria

Clinically significant abnormal quantitative vital signs measurements will be identified in accordance with the following clinically significant abnormal criteria:

**Table 3 : Clinically Significant Abnormal Criteria of Vital Signs**

Variable	Unit	Visit	Low	High
Systolic	mmHg	Baseline	< 90 mmHg	> 180 mmHg

Document:

Author:

Version Number:

Version Date:

Final v1.0

10Sep2019

Template No: CS\_TP\_BS016 Revision 4

Effective Date: 01Apr2016

Reference: CS\_WI\_BS005

blood pressure		Post-baseline	≤ 90 mmHg AND change from baseline ≤ -20 mmHg	≥ 180 mmHg AND change from baseline ≥ 20 mmHg
Diastolic blood pressure	mmHg	Baseline	< 50 mmHg	> 110 mmHg
		Post-baseline	≤ 50 mmHg AND change from baseline ≤ -15 mmHg	≥ 105 mmHg AND change from baseline ≥ 15 mmHg
Pulse	beats/min	Baseline	< 50 beats/min	> 120 beats/min
		Post-baseline	≤ 50 beats/min AND change from baseline ≤ -15 beats/min	≥ 120 beats/min AND change from baseline ≥ 15 beats/min
Body temperature	°C	Baseline	< 35.0 °C	> 38.3 °C
		Post-baseline	≤ 35.0 °C AND change from baseline ≤ -1.1 °C	≥ 38.3 °C AND change from baseline ≥ 1.1 °C
Respiratory rate	breaths/min	Baseline	≤ 10 breaths/min	≥ 24 breaths/min
		Post-baseline	≤ 10 breaths/min	≥ 24 breaths/min
Weight	kg	Baseline	None	None
		Post-baseline	percentage change from baseline ≤ -7.0 %	percentage change from baseline ≥ 7.0 %

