8.9.4 Vital Signs Measurements, Physical Findings and Other Safety Evaluations

Summary statistics will be presented for results at each visit with vital sign assessments and at EOS, as well as for change from baseline results to each visit with vital sign assessments and EOS for systolic and diastolic blood pressure, respiratory rate, body temperature, and pulse.

The overall incidence of vital sign abnormalities will also be presented. Patients will be counted at most once for an abnormality for each vital sign parameter.

A listing of all vital sign abnormalities will be presented for the SAF. Criteria used to define abnormal vital sign results will be defined in the SAP. Shifts (abnormal low, normal, and abnormal high) from baseline to each post-baseline visit with vital sign assessments and EOS, based on normal ranges, will be presented for vital sign parameters.

A table and listing of any ECG abnormalities at screening will be presented.

A listing of physical examination abnormalities will be presented.

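### The vital-sign shift table judges baseline by a limit and later values by a limit plus a change, so some unchanged or modestly worse abnormal values appear as shifts to normal

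*SAP*

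**What the plan says.** SAP section 17.5 asks for a "Shift table of incidence of significant abnormal values (low, normal, high), based on the criteria listed as below, from baseline to each post-baseline visit". The criteria are those of Table 3.

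At baseline, Table 3 uses a plain limit: systolic below 90 or above 180 mmHg, diastolic below 50 or above 110 mmHg, pulse below 50 or above 120 beats/min, temperature below 35.0 or above 38.3 °C. After baseline it adds a required change:

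- systolic: "≤ 90 mmHg AND change from baseline ≤ -20 mmHg" (low) and "≥ 180 mmHg AND change from baseline ≥ 20 mmHg" (high)
- diastolic: "≤ 50 mmHg AND change from baseline ≤ -15 mmHg" (low) and "≥ 105 mmHg AND change from baseline ≥ 15 mmHg" (high)
- pulse: "≤ 50 beats/min AND change from baseline ≤ -15 beats/min" (low) and "≥ 120 beats/min AND change from baseline ≥ 15 beats/min" (high)
- temperature: at or below 35.0 °C with a fall of at least 1.1 °C (low), or at or above 38.3 °C with a rise of at least 1.1 °C (high)

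Respiratory rate has identical limits at both times. Weight has no baseline criterion.

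Section 17.5 also reports abnormalities by visit and overall. A patient is overall normal when no post-baseline result is abnormal, whatever the baseline value was.

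Protocol section 8.9.4 leaves the definition of an abnormal vital sign to the SAP, but describes the shift table separately: "Shifts (abnormal low, normal, and abnormal high) from baseline to each post-baseline visit with vital sign assessments and EOS, based on normal ranges". SAP section 2.6, which lists changes from the protocol, mentions only the PK, PD and per-protocol sets.

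**The concern.** The cells of a shift table mean 'stayed' or 'moved' only if the same ruler is used at both ends. Here the rows use a limit and the columns use a limit plus a change. A patient who starts outside the limit and has not moved cannot satisfy the change condition, and the only category left is normal. The table then shows an improvement that did not happen.

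The same rule feeds the abnormality counts and the H/L flags in the listing. Protocol section 6.4.6 names hypotension and fever among the features of infusion reactions, which are events of special interest, so vital-sign tables are a place where a reader will look.

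**Working it through.** This is a check of a classification rule; the plan states no figure to reproduce. The inputs are the Table 3 limits and changes given above.

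**Rule, using low values as the example.** Let *b* be the baseline value, *v* the later value, *L* the limit and *d* the required change. Baseline is Low if *b* < *L*. Post-baseline is Low if *v* ≤ *L* and *v* − *b* ≤ −*d*. High values mirror this. Anything else is Normal.

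**Unchanged abnormal value.** If *v* = *b*, the change is 0. Since *d* is 20, 15, 15 or 1.1, the change condition fails. Every abnormal baseline that stays the same is therefore tabulated as Normal, for all four parameters and in both directions.

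**Worsening by less than *d*.**

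| Parameter | Baseline → later | Baseline class | Beyond the later limit? | Change vs required | Later class |
|---|---|---|---|---|---|
| Systolic (mmHg) | 88 → 70 | Low (< 90) | yes (≤ 90) | −18 vs −20 | Normal |
| Systolic (mmHg) | 185 → 204 | High (> 180) | yes (≥ 180) | +19 vs +20 | Normal |
| Pulse (beats/min) | 121 → 135 | High (> 120) | yes (≥ 120) | +14 vs +15 | Normal |
| Temperature (°C) | 38.4 → 39.4 | High (> 38.3) | yes (≥ 38.3) | +1.0 vs +1.1 | Normal |

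In whole units (0.1 °C steps for temperature), the largest worsening still tabulated as Normal is 19 mmHg systolic, 14 mmHg diastolic, 14 beats/min and 1.0 °C.

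**Where the rule does flag.** Systolic 85 → 65 is a change of −20, so it is Low to Low; 185 → 205 is +20, so it is High to High.

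**Normal baseline.** The change condition also acts here. Systolic 95 → 80 is a change of −15, so it is Normal to Normal although 80 is below 90.

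**One limit at both times.** Applying Table 3's baseline systolic limits at both times, purely as an illustration, gives 85 → 85, 85 → 70 and 85 → 66 as Low to Low; 185 → 185 and 185 → 204 as High to High; and 95 → 80 as Normal to Low.

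**Limits that differ within Table 3.** Diastolic high is > 110 at baseline but ≥ 105 (plus change) afterwards. A later value of 107 reached from 92 (+15) is High, although 107 at baseline would be Normal. For all four parameters the inequalities are strict at baseline and non-strict afterwards.

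**Comparison inside the SAP.** Laboratory shifts in section 17.3 use the laboratory reference range at both times, and respiratory rate in Table 3 uses one pair of limits. The mismatch is therefore not the SAP's general practice.

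**The case against.** The best defence is that the protocol hands the definition of abnormal to the SAP, and that the SAP labels both the shift table and Table 3 as concerning significant abnormality. On that reading, 'normal' means only that the clinically significant criterion was not met. The delegation is real and the label helps. But protocol section 8.9.4 makes a separate statement on what the shifts rest on, and neither the delegation nor SAP section 2.6 reconciles it with Table 3. The printed category is still 'normal'.

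The second defence is that little depends on it, and this largely stands:

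- Eligibility makes several abnormal baselines unlikely: uncontrolled or severe hypertension, uncontrolled arrhythmia and acute severe infection are excluded, and patients must have no B symptoms. No criterion names low blood pressure.
- Actual values and changes are summarised by visit and time point, and all vital signs are listed.
- Clinically relevant findings go in as adverse events (protocol section 5.2.3), and infusion reactions are summarised separately (SAP section 17.1).
- SAP section 17 plans no between-group safety comparison, and the rule is the same in both arms.

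A reader might infer more than the documents support:

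- *That all worsening is hidden.* Only worsening short of the change threshold is.
- *That every patient with an abnormal baseline and a small later change is misreported.* Some truly normalise: systolic 85 → 100 changes by 15 and is rightly Normal.
- *That one such reading makes a patient overall normal.* That label requires that no post-baseline reading meets the rule, and vital signs are taken three times per infusion and at every follow-up visit.
- *That the protocol prescribes Table 3's absolute limits.* It refers to normal ranges, and neither document gives any for vital signs.
- *That infusion reactions would be missed.* A large fall from a normal baseline, such as 120 → 85 mmHg (−35), is still flagged.

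**Conclusion.** The point holds, as a minor one. For systolic pressure, diastolic pressure, pulse and temperature, the shift table will show a patient who starts beyond the limit as moving to normal when the value is unchanged or has worsened by less than 20 mmHg, 15 mmHg, 15 beats/min or 1.1 °C respectively. A patient whose post-baseline readings all fail the limit-plus-change rule is counted overall normal, even if some lie beyond the limit. Respiratory rate is unaffected, and weight has no baseline class to shift from.

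This assumes that Table 3 is applied as written and that the abnormality counts use it too; section 17.5 offers no other criteria. The number of patients cannot be derived, because the share starting outside the limits is not given; the eligibility criteria suggest that it is small. No efficacy, PK or equivalence conclusion is touched, and the underlying values, changes and adverse events are still reported.

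**What to change.** In the shift table and the overall normal/abnormal count, class baseline and post-baseline values by one set of limits written into the SAP: the normal ranges to which protocol section 8.9.4 refers, which the SAP must first specify. In doing so, reconcile the differing limits in Table 3 (diastolic high > 110 against ≥ 105, and strict against non-strict inequalities). Which values to adopt is a clinical decision for the sponsor.

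Report the limit-plus-change rule separately, as a count of clinically significant post-baseline changes, and state which rule drives the H/L flags in the listing.

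If the sponsor prefers to keep the present table, list it in SAP section 2.6 as a departure from the protocol and rename the normal category to say that the criteria were not met. That cures the label but not the mismatch between rows and columns.

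The cost is SAP wording, minor programming and one extra table. No new data are needed.
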